5.1 Management of Optical Correction

A refraction should be performed at any time the investigator suspects that refractive error may not be optimally corrected. A change in spectacle correction is at investigator discretion.

5.2 Management of Strabismus

Strabismus surgery should not be done until after the primary outcome visit has been completed. Surgery will be recorded in the comment section of the Follow-up Examination Form.

5.3 Worsening of Visual Acuity in the Amblyopic Eye

If visual acuity should worsen in the amblyopic eye, the investigator should evaluate this condition using best clinical judgment and perform whatever work-up is clinically indicated to assess for an alternate cause (i.e., other than amblyopia) for the visual loss. Patients found to have a cause other than amblyopia that fully explains the visual loss (i.e., amblyopia was never present) will be dropped from the study.

5.4 Patient Withdrawals

A parent or guardian may withdraw a patient from the trial at any time. This is expected to be a very infrequent occurrence in this trial in view of the testing procedures' similarity to routine clinical practice. If the parents or guardian indicate that they want to withdraw the child from the study, the investigator should attempt to speak with them to determine the reason.

5.5 Risks

There are no risks involved in this study that would not be part of usual care in which the study treatments were administered.

5.5.1 Risks of Examination Procedures

The procedures in this study are part of daily pediatric eye care practice in the United States and pose no known risks. As part of a routine usual-care exam, the patient may receive cycloplegic/dilating eye drops.

5.5.2 Risks of Patching

If skin irritation occurs, the parent will be advised to put an emollient on the skin and discontinue use of the patch for a day.

Patching could potentially decrease the visual acuity in the sound eye, although this is almost always reversible. However, this occurrence is extremely unlikely since the sound eye will have several hours without occlusion each day. The diagnosis and management of reverse amblyopia is left to the investigator's judgment.

Patching could precipitate the development of an ocular deviation (strabismus), although this has been found to be very rare in our previous studies and indistinguishable from the natural history of strabismus. If treatment precipitates the development of an ocular deviation (e.g., esotropia in child with hyperopia), the parent will be advised to have the patient see the investigator as soon as possible.

415 **5.5.3 Risk Assessment**

416 It is the investigators' opinion that the protocol's level of risk falls under DHHS 46.404 which is
417 research not involving greater than minimal risk.

418
419 **5.6 Reporting of Adverse Events**

420 Each investigator is responsible for informing his/her IRB of serious treatment-related adverse events
421 and for abiding by any other reporting requirements specific to his/her IRB.

422 Data on the complications of the study treatments will be tabulated regularly by the Coordinating
423 Center for review by the Data and Safety Monitoring Committee. Serious, treatment-related
424 complications will be reported expeditiously to the Data and Safety Monitoring Committee, which will
425 receive a full adverse event report semi-annually. Following each DSMC data review, a summary will
426 be provided to IRBs.

427

428 **5.7 Patient Payments**

429 The parent/guardian of each patient will be compensated \$30 for each run-in phase follow-up visit, and
430 \$30 per visit for completion of the randomization visit and the 10-week primary outcome visit. For
431 patients remaining in follow-up after the 10-week visit, \$30 will be paid for each 10-week interval
432 visit, up to an additional \$120 (4 exams). If there are extenuating circumstances, additional funds may
433 be provided for travel if expenses exceed \$30 and the patient will be unable to complete the visit
434 without reimbursement of travel expenses. All payments will be made by the Jaeb Center in the month
435 following the date of each completed visit.

436

437 **5.8 Study Costs**

438 The eye patches will be provided by the study at no cost. The study will pay for visits and testing that
439 would not be done if the patient was not part of the study (research related visits). The patient or
440 his/her insurance company will be responsible for the costs of visits that would be needed whether they
441 were in the study or not (standard care visits).

442

443 **5.9 Discontinuation of Study**

444 The study may be discontinued by the Steering Committee (with approval of the Data and Safety
445 Monitoring Committee) prior to the preplanned completion of enrollment and follow-up for all
446 patients.

447

448 **5.10 Contacts by the Jaeb Center for Health Research**

449 The Jaeb Center serves as the PEDIG Coordinating Center. The Jaeb Center will be provided with the
450 parent/guardian's contact information. The Jaeb Center will maintain direct contact with the parents or
451 guardian of each patient. Permission for such contacts will be included in the Informed Consent Form.
452 The principal purpose of the contacts will be to develop and maintain rapport with the family and to
453 help coordinate scheduling of the outcome examination. One phone contact is planned for each patient
454 5 weeks after randomization. Additional phone contacts will be made if necessary to facilitate the
455 scheduling of the patient for follow-up visits. A patient newsletter, study updates, and a study logo
456 item may be sent. Patients will be provided with a summary of the study results in a newsletter format
457 after completion of the study by all patients.

458

Chapter 6: Sample Size Estimation and Statistical Analysis

The approach to sample size and statistical analyses are summarized below. A detailed statistical analysis plan will be written and finalized prior to the completion of the study. The analysis plan synopsis in this chapter contains the framework of the anticipated final analysis plan, which will supersede these sections when it is finalized.

6.1 Primary Analysis for Efficacy

The study is evaluating 2 management approaches for amblyopia in patients already treated with an average of 2 hours of patching per day:

1. Continued 2 hours per day of patching
2. Increase in patching intensity to 42 hours per week (average of 6 hours per day)

The primary analysis will be a treatment group comparison of logMAR visual acuity scores obtained 10 weeks after randomization, adjusted for baseline acuity scores in an analysis of covariance (ANCOVA) model.

The primary analysis will follow the intent-to-treat principle. Data will be included only from patients who complete the 10-week outcome. There will be no imputation of data for patients who are lost to follow-up or withdraw from the study prior to the 10-week outcome. In a secondary analysis, imputation methods for missing data will be assessed (such as last-observation-carried-forward and multiple imputation) for consistency with the primary analysis. A separate analysis also will be conducted including only patients whose outcome exams were performed within the time window for the visit.

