74 least 6 weeks apart, confirmed by a re-test, and patients have received at least 12 weeks of two hours

75 daily patching.

76

77 Randomized Treatment Groups

78 When there has been no improvement with two hours daily patching, eligible patients will be

79 randomized to one of two treatment regimens:

- 80 • Intensified treatment: 42 hours per week of patching (averaging 6 hours daily)
- 81 • Control: 2 hours daily patching
- 82

83 Sample Size

84 Seventy-nine patients will be randomized in each of the two treatment groups, for a total of 158

85 patients. This sample size has 90% power to detect a difference if the true difference in change from

86 baseline between groups is 0.075 logMAR at 10 weeks, with 2-sided type I error of 5%.

87

88 RCT Contact and Visit Schedule

- 89 • Phone call 5 weeks after randomization
- 90 • Primary outcome visit 10 weeks after randomization
- 91 • If amblyopic eye acuity improved by ≥ 1 line at primary outcome, follow-up visits at 10 week
- 92 intervals until no improvement of one or more lines, confirmed by a re-test

93

94 Primary Analysis

95 The primary outcome is amblyopic eye visual acuity 10 weeks after randomization.

[figure not shown]
96

97 The primary analytic approach for the amblyopic eye acuity will be a treatment group comparison of
98 the mean amblyopic eye acuity adjusted for baseline acuity using an analysis of covariance.

99

100 **1.4 Study Summary Flow Chart**

101

102

103

Chapter 2: Patient Enrollment

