4.2 Randomization of Eligible Patients

1. Once a patient is randomized, that patient will be included in the analysis regardless of whether the assigned treatment is received or not. Thus, the investigator must not randomize a patient until he/she is convinced that the parent/guardian will accept and comply with either of the treatment regimens. Regardless of whether the patient receives the assigned treatment or not, the patient is still considered enrolled in the study and every effort should be made to perform the follow-up examinations according to the study protocol.
2. The Jaeb Center will construct a Master Randomization List using a permuted block design stratified by site, which will specify the order of treatment group assignments. A patient is officially enrolled when the website randomization process is completed.

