6.2 Secondary Efficacy Analyses

6.2.1 Visual Acuity Defined as a Binary Outcome

A secondary analysis will be a treatment group comparison of the proportion of patients who have improved by 2 or more logMAR visual acuity lines 10 weeks after randomization for each treatment group, adjusted for baseline acuity scores using logistic regression.

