6.2.2 Follow-up after the Primary Outcome

Patients in both groups who have improved by 1 or more lines from baseline to the 10-week outcome exam will continue in the study. Visits will occur every 10 ± 1 weeks until no improvement of one or more lines from the previous visit is seen. A secondary analysis will be a treatment group comparison of the proportion of patients with at least 2 logMAR lines of visual acuity improvement between randomization and the visual acuity at the last study visit using logistic regression, adjusting for baseline visual acuity. An additional secondary analysis will be a treatment group comparison of logMAR visual acuity scores in the amblyopic eye at last study visit, adjusted for baseline visual acuity scores in an analysis of covariance (ANCOVA) model.

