539 week visits, we assumed a standard deviation for the change from baseline to 10-week outcome score
540 in this study of 0.14 logMAR. We will use a two-sided alpha of 0.05, with 90% power to detect a
541 difference if the true difference in change from baseline between groups was 0.075 logMAR at 10
542 weeks. With these assumptions, and accounting for 5% loss to follow-up, we have calculated a
543 necessary sample size of 158 patients.

544
545 A minimum of 158 patients are expected to be enrolled with a goal to enroll an appropriate
546 representation of minorities. As the enrollment goal approaches, sites will be notified of the end date
547 for recruitment. Patients who have signed an informed consent form can be randomized up until the
548 end date, which means the minimum recruitment goal might be exceeded. The maximum number of
549 randomized patients will be 178.

550
551

552 **6.5 Interim Analysis and Sample Size Re-estimation**

553 We are unaware of any previous literature reporting on the response to intensified treatment of
554 amblyopia after improvement stops with initial treatment. The sample size estimates above are based
555 on a study of the initial treatment of amblyopia and may not match our definition of no improvement in
556 acuity in the current study. Although we feel we have been conservative in our estimate of variation, a
557 sample size re-estimation will be performed once 50% of the originally planned number of patients
558 have completed the 10-week primary outcome visit. A pooled estimate of variance without respect to
559 treatment group will be calculated and used to re-estimate sample size using a procedure that maintains
560 masking.⁵ An adjustment will be made to the final alpha based upon this interim sample size re-
561 estimation.
562

563
564
565
566
567
568
569
570
571
572
573
574
575
576
577

Chapter 7: References

1. Pediatric Eye Disease Investigator Group. A randomized trial of atropine vs patching for treatment of moderate amblyopia in children. Arch Ophthalmol 2002;120:268-78.
2. Pediatric Eye Disease Investigator Group. A randomized trial of atropine regimens for treatment of moderate amblyopia in children. Ophthalmology 2004;111:2076-85.
3. Pediatric Eye Disease Investigator Group. A randomized trial to evaluate 2 hours of daily patching for strabismic and anisometropic amblyopia in children. Ophthalmology 2006;113:904-12.

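### Randomization is stratified by site but the two ANCOVA models leave site out; if outcomes vary by site, their standard errors are slightly too large (minor, costless to fix)

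*Protocol*

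**What the plan says.** Section 4.2 has the coordinating center prepare a "Master Randomization List using a permuted block design stratified by site". No other stratification factor is named, and the block size is not given.

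The synopsis (Section 1.3) describes the primary analysis as a comparison of "the mean amblyopic eye acuity adjusted for baseline acuity using an analysis of covariance". Section 6.1 repeats this: 10-week logMAR scores are compared between groups, "adjusted for baseline acuity scores in an analysis of covariance (ANCOVA) model". Section 6.2.2 plans the same kind of ANCOVA for acuity at the last study visit. The binary outcomes are handled in the same way: the 10-week responder model in Section 6.2.1 is "adjusted for baseline acuity scores using logistic regression", and the last-visit model in Section 6.2.2 is fitted "using logistic regression, adjusting for baseline visual acuity".

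No section names site as a covariate, stratum or random effect, or explains its omission. The opening paragraph of Chapter 6 describes the chapter as a synopsis and framework for a detailed analysis plan, "which will supersede these sections when it is finalized".

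**The concern.** The protocol states its adjustment set explicitly and repeatedly, and that set omits the one factor on which the allocation is balanced.

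Stratified blocking makes the arms nearly equal in size within each site. Site-to-site differences in outcome then contribute little to the real variability of the treatment difference. An ANCOVA without site does not know this: it counts those differences as residual noise and computes its standard error as if allocation had been unrestricted. If sites do differ, the reported standard error exceeds the real one. At stake are a slightly wide interval for the 10-week difference and a test that rejects less often than its nominal 5%.

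**Working it through.** **Inputs.** Section 6.4 gives an SD of 0.14 logMAR, a difference of 0.075 logMAR, two-sided alpha 0.05, 90% power and 5% loss. Section 1.3 gives 79 patients per group. The protocol gives no number of sites, block size or intra-site correlation (ICC). These are assumed below: 15, 30 or 50 sites of unequal size, blocks of 4, ICC from 0 to 0.20. The 0.14 is treated as the total residual SD.

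**Step 1: the planned sample size.** Normal approximation: n per arm = 2(1.960 + 1.282)² × 0.14² / 0.075² = 73.2, so 74. The exact noncentral-t calculation gives 75. Then 75 / 0.95 = 78.9, so 79 per arm and 158 in total, as stated. Power with 75 analysed per arm is 90.3%. No site adjustment enters this figure.

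**Step 2: standard error of the planned model.** SE = 0.14 × √(2/75) = 0.0229 logMAR. The 95% half-width is 1.96 × 0.0229 = 0.045.

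**Step 3: size of the overstatement.** In the ideal case site takes a share ICC out of the variance. The SE with site, divided by the SE without, is then √(1 − ICC). This was checked by simulating a random site intercept fitted by REML (158 randomized, 5% loss, 2,500 runs per setting). The overstatement is 1/ratio − 1.

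| Assumed ICC | √(1 − ICC) | Simulated SE ratio, 15 / 30 / 50 sites | SE overstated by (simulated) |
|---|---|---|---|
| 0 | 1.000 | 0.994 / 0.993 / 0.992 | see below |
| 0.02 | 0.990 | 0.988 / 0.987 / 0.987 | 1.2–1.3% |
| 0.05 | 0.975 | 0.977 / 0.976 / 0.977 | 2.4–2.5% |
| 0.10 | 0.949 | 0.957 / 0.956 / 0.958 | 4.4–4.6% |
| 0.20 | 0.894 | 0.909 / 0.909 / 0.915 | 9–10% |

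The fall of under 1% at ICC 0 is not a real gain, since there is then no site variation to remove. On the 0.045 half-width, ICC 0.05 means about 0.977 × 0.0448 = 0.0438, and ICC 0.10 about 0.957 × 0.0448 = 0.0429. The interval narrows by 0.001 to 0.002 logMAR on each side.

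**Step 4: validity.** In these simulations the two-sided type I error was 0.026 to 0.051 without site and 0.042 to 0.055 with the random intercept. A separate simulation of the planned ANCOVA gave 0.029 to 0.054, with the lowest values (0.029 to 0.033) at ICC 0.20 with 15 or 30 sites. The planned test errs, if at all, on the conservative side. With the random intercept, power at 0.075 logMAR was equal or higher in every setting, by up to about 3 points at ICC 0.20.

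**Step 5: does the estimate itself improve?** Hardly. In a further simulation of the random intercept (2,000 runs per setting, no baseline covariate), the actual spread of the estimates under the two models was 0.02236 against 0.02233 (15 sites, ICC 0.05) and 0.02181 against 0.02178 (30 sites, ICC 0.10). What changes is the reported SE.

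**Step 6: why not fixed site effects.** Mean SE without site, then with fixed site effects:

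| Sites | ICC 0 | ICC 0.05 | ICC 0.10 | ICC 0.20 |
|---|---|---|---|---|
| 15 | 0.0229, 0.0231 | 0.0228, 0.0226 | 0.0229, 0.0220 | 0.0227, 0.0207 |
| 30 | 0.0230, 0.0238 | 0.0228, 0.0230 | 0.0229, 0.0225 | 0.0228, 0.0212 |
| 50 | 0.0229, 0.0246 | 0.0229, 0.0240 | 0.0229, 0.0233 | 0.0228, 0.0220 |

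The change runs from about +7% (0.0246/0.0229) to −9% (0.0207/0.0227). Its sign depends on quantities that the protocol does not give. The random intercept did not raise the mean SE in any setting.

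**The case against.** The strongest reply is that this belongs to the analysis plan. Chapter 6 calls itself a synopsis to be superseded, and naming one covariate does not rule out another. That lowers the importance of the point but does not remove it: the protocol sets out a specific model as the framework for the final plan, and that model does not follow the allocation scheme.

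Second, the protocol limits several sources of site variation. Acuity is measured by a standard protocol on certified testers, with a masked examiner at 10 weeks (Section 4.3). Spectacle correction has numeric criteria (Section 2.2), a minimum level of compliance is required before randomization (Section 3.2), and the coordinating center makes the 5-week call (Section 4.3.1). This stands, and it makes the lower ICCs more plausible than 0.10 or 0.20. It also means that the new term may often do nothing: the site variance was estimated as zero in about 42% of simulated trials at ICC 0.02 and in 22–24% at 0.05.

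Third, adjustment might cost precision. That is true of fixed effects with many small sites, but not of the random intercept proposed here.

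**Conclusion.** The point holds as a minor one, for the primary ANCOVA and the last-visit ANCOVA. If outcomes vary by site, their model standard errors are overstated by about 1%, 2.5% or 4.5% at ICCs of 0.02, 0.05 or 0.10. These ICCs, the site counts and the block size are assumptions; with no site variation there is no overstatement.

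Four stronger readings are tempting, and none is supported:

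- **That the planned analysis is biased or invalid.** It is neither. Omitting site can only make the ANCOVA test conservative.
- **That the sample size is wrong.** The 158 reproduces exactly without site in the model.
- **That patient information is lost.** The formula 1/(1 − ICC) − 1 gives 2.0%, 5.3% and 11.1%, which could be read as wasted patients. But stratification already protects the estimate, whose real spread barely changes; only its reported precision is affected.
- **That the logistic models share the fault.** Adding a prognostic factor to a logistic model does not shrink the SE of the log odds ratio and usually enlarges it. A site intercept would also change the target to a site-conditional odds ratio.

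**What to change.** In Section 6.1, and correspondingly in the synopsis in Section 1.3, add site as a random intercept to the primary ANCOVA. Do the same for the ANCOVA in Section 6.2.2. Keep the model without site as a sensitivity analysis. Do not use fixed site effects, and leave the logistic models in Sections 6.2.1 and 6.2.2 as planned.

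The cost is one phrase in each place and no extra data, because site is already recorded for randomization. If the site variance is estimated as zero, the fit reduces to the planned model. Section 6.2.3 repeats the primary analysis within subgroups and would inherit the term. The choice should be fixed when the analysis plan is finalized, so that it is not made among fitted models later.

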6.2 Secondary Efficacy Analyses

6.2.1 Visual Acuity Defined as a Binary Outcome

A secondary analysis will be a treatment group comparison of the proportion of patients who have improved by 2 or more logMAR visual acuity lines 10 weeks after randomization for each treatment group, adjusted for baseline acuity scores using logistic regression.

6.2.2 Follow-up after the Primary Outcome

Patients in both groups who have improved by 1 or more lines from baseline to the 10-week outcome exam will continue in the study. Visits will occur every 10 ± 1 weeks until no improvement of one or more lines from the previous visit is seen. A secondary analysis will be a treatment group comparison of the proportion of patients with at least 2 logMAR lines of visual acuity improvement between randomization and the visual acuity at the last study visit using logistic regression, adjusting for baseline visual acuity. An additional secondary analysis will be a treatment group comparison of logMAR visual acuity scores in the amblyopic eye at last study visit, adjusted for baseline visual acuity scores in an analysis of covariance (ANCOVA) model.

6.2.3 Treatment Effect in Subgroups

The treatment effect in subgroups based on baseline factors will also be assessed in exploratory analyses. Interpretation of subgroup analyses will depend on whether the overall analysis demonstrates a significant treatment group difference. In the absence of an overall study difference, these subgroup analyses will be interpreted with caution.

507 The subgroups of interest are those based on visual acuity at the time of randomization, visual acuity at
508 the time of initial treatment, cause of amblyopia, length of prior treatment with 2 hours of patching,
509 and age at randomization.

510
511 In accordance with NIH guidelines, a subgroup analysis of treatment effect according to gender, as
512 well as race/ethnicity, will be conducted. However, based on results from previous ATS studies, a
513 treatment effect by these variables is not expected.

514
515 The general approach for these exploratory analyses will be to repeat the primary analysis within each
516 subgroup.

517 518 **6.2.4 Stereoacuity**

519 Differences between treatment groups in stereoacuity at the 10-week outcome will be assessed using a
520 comparison of the distributions with the exact Wilcoxon rank sum test.

521 522 **6.3 Primary Analysis for Safety**

523 **6.3.1 Sound Eye Acuity Data**

524 The loss of 2 or more lines in sound eye visual acuity from baseline to the 10-week masked exam will
525 be tabulated for each treatment group.

526 527 **6.3.2 Ocular Alignment**

528 Ocular alignment will be assessed at baseline and at 10 weeks after randomization. Development of
529 new strabismus (no tropia at baseline and the presence of near and/or distance tropia at follow-up) or
530 an increase from baseline ≥ 10 PD will be tabulated by treatment group. Similarly, disappearance of a
531 heterotropia and a decrease in the angle of a preexisting strabismus by ≥ 10 PD will be tabulated.

532 533 **6.4 Sample Size**

534 We are unaware of any previous literature on the response to treatment of amblyopia still present after
535 initial treatment. The sample size calculations were based on amblyopic eye visual acuity data in a
536 cohort of patients initially treated with 2 hours per day of patching from our previous ATS6 study.⁴ In
537 that study, patients were seen at 2, 5, 8, and 17 weeks after randomization. Based on improvement in
538 visual acuity between 8 and 17 weeks among patients defined as stable across the initial 2, 5, and 8
539 week visits, we assumed a standard deviation for the change from baseline to 10-week outcome score
540 in this study of 0.14 logMAR. We will use a two-sided alpha of 0.05, with 90% power to detect a
541 difference if the true difference in change from baseline between groups was 0.075 logMAR at 10
542 weeks. With these assumptions, and accounting for 5% loss to follow-up, we have calculated a
543 necessary sample size of 158 patients.

544
545 A minimum of 158 patients are expected to be enrolled with a goal to enroll an appropriate
546 representation of minorities. As the enrollment goal approaches, sites will be notified of the end date
547 for recruitment. Patients who have signed an informed consent form can be randomized up until the
548 end date, which means the minimum recruitment goal might be exceeded. The maximum number of
549 randomized patients will be 178.

550
551

552 **6.5 Interim Analysis and Sample Size Re-estimation**

553 We are unaware of any previous literature reporting on the response to intensified treatment of
554 amblyopia after improvement stops with initial treatment. The sample size estimates above are based
555 on a study of the initial treatment of amblyopia and may not match our definition of no improvement in
556 acuity in the current study. Although we feel we have been conservative in our estimate of variation, a
557 sample size re-estimation will be performed once 50% of the originally planned number of patients
558 have completed the 10-week primary outcome visit. A pooled estimate of variance without respect to
559 treatment group will be calculated and used to re-estimate sample size using a procedure that maintains
560 masking.⁵ An adjustment will be made to the final alpha based upon this interim sample size re-
561 estimation.
562

563
564
565
566
567
568
569
570
571
572
573
574
575
576
577

Chapter 7: References

1. Pediatric Eye Disease Investigator Group. A randomized trial of atropine vs patching for treatment of moderate amblyopia in children. Arch Ophthalmol 2002;120:268-78.
2. Pediatric Eye Disease Investigator Group. A randomized trial of atropine regimens for treatment of moderate amblyopia in children. Ophthalmology 2004;111:2076-85.
3. Pediatric Eye Disease Investigator Group. A randomized trial to evaluate 2 hours of daily patching for strabismic and anisometropic amblyopia in children. Ophthalmology 2006;113:904-12.

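### Section 6.2.3 repeats the primary ANCOVA within each subgroup and names no interaction test, so the stated method cannot show whether the treatment effect differs between subgroups

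*Protocol*

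**What the plan says.** Section 6.2.3 presents the subgroup work as exploratory: "The treatment effect in subgroups based on baseline factors will also be assessed in exploratory analyses". It names five factors of interest: acuity at randomization, acuity at initial treatment, cause of amblyopia, length of prior 2-hour patching, and age at randomization. It adds gender and race/ethnicity under NIH guidelines and says that no effect by these two is expected. That makes seven factors.

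The method is then stated: "The general approach for these exploratory analyses will be to repeat the primary analysis within each" subgroup. The analysis to be repeated is the one in section 6.1, a comparison of 10-week logMAR acuity "adjusted for baseline acuity scores in an analysis of covariance (ANCOVA) model". No treatment-by-factor term, no other direct comparison of effects between subgroups, and no multiplicity control is mentioned.

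Interpretation is tied to the overall result: "In the absence of an overall study difference, these subgroup analyses will be interpreted with caution". Nothing equivalent is said for a positive overall result. The introduction to Chapter 6 describes the chapter as a framework that a later statistical analysis plan will supersede.

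**The concern.** The question behind a subgroup analysis is whether the effect of longer patching varies with a baseline factor. The section treats it that way itself when it gives an expectation for gender and race/ethnicity. Repeating the ANCOVA inside each stratum answers another question: is the effect in this stratum distinguishable from zero? Each stratum has fewer patients than the trial, so a uniform effect will often reach p<0.05 in one stratum and miss it in the other by chance.

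Such contrasts are most frequent when treatment works, which is the case where the text asks for no explicit caution. At stake is a published statement that more patching helps, say, younger or anisometropic children but not others, when the effect is the same in all of them.

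**Working it through.** **Inputs.** From Protocol section 6.4: two-sided alpha 0.05, 90% power, difference 0.075 logMAR, SD of change 0.14, 5% loss, 158 patients. From section 1.3: 79 per group. Assumed, because the protocol does not give them: two levels per factor, the split fractions, independence between factors, and SD 0.14 used as the residual SD.

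**The plan's own figure.** Normal approximation: n = 2(1.960 + 1.282)² × 0.14² / 0.075² = 73.2, so 74 per arm. The t-based calculation gives 75 per arm (power 90.3%). 75 / 0.95 = 78.9, so 79 per arm and 158 in total. The stated size is reproduced, and about 75 completers per arm is the right basis for what follows.

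**Power in half the sample, uniform effect 0.075.** With 37.5 per arm, SE = 0.14 × √(2/37.5) = 0.0323. Power = Φ(0.075/0.0323 − 1.960) = Φ(0.36) = 64% (noncentral t: 63%).

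**Chance of discordant p-values for one factor.** With powers a and b in the two strata, P = a(1 − b) + b(1 − a).

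| Split | Power in each stratum | One significant, one not |
|---|---|---|
| 50:50 | 64% / 64% | 46% |
| 60:40 | 72% / 55% | 48% |
| 70:30 | 78% / 44% | 54% |
| 80:20 | 84% / 31% | 63% |

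**Across several factors.** All factors divide the same patients, so the per-factor chances cannot be multiplied; 1 − (1 − 0.461)⁷ = 99% would be too high. Simulation of whole trials gives at least one discordant factor among seven in 84% to 86% of trials at 50:50 and 94% to 95% at 70:30. Among trials with a significant overall result, one simulation gave 85% and 96% for these two splits. For the five factors of interest at 50:50 it is 79% to 81%. A latent correlation of 0.5 between all seven factors still leaves about 83% to 84% at 50:50.

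**Interaction test on the same data.** Under a uniform effect the false-signal rate is 5% per factor by construction. Across seven factors, 1 − 0.95⁷ = 30%, and the simulations agree.

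**No true effect.** Discordance per factor is 2 × 0.05 × 0.95 = 9.5%. Across seven factors about 33% of trials have a discordant factor, and 34% to 36% have at least one significant subgroup. Unadjusted interaction tests give at least one false signal in about 30%.

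**Power of the interaction test.** At 50:50, SE of the difference in effects = 0.14 × √(2/37.5 + 2/37.5) = 0.0457. For a difference in effect of 0.075 logMAR, power = Φ(0.075/0.0457 − 1.960) = Φ(−0.32) ≈ 38%. The difference detectable with 80% power is (1.960 + 0.842) × 0.0457 = 0.128 logMAR.

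**The case against.** The strongest reply is that this is provisional text. Chapter 6 is a synopsis to be superseded, and interaction terms are often specified only in the analysis plan. That would answer a silent protocol. This one is not silent: it names a general approach, and the approach does not fit the question. A framework carries forward unless it is changed.

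Three stronger readings are tempting, and the documents do not support them. First, a reader might infer that the protocol rules out interaction tests, or that it prescribes judging subgroups by comparing p-values. It does neither. It only fails to mention the one and is open to the other, and within-subgroup estimates are useful as description. Second, a reader might take the conditional caution as the sole safeguard. The exploratory label and the stated expectation for gender and race/ethnicity are safeguards too, though neither supplies a test of whether effects differ. Third, a reader might cite the share of null trials with a significant subgroup as a main harm. Most such trials have a null overall result, where caution is already required, and unadjusted interaction tests improve the figure only slightly.

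It is also fair to say that the split sizes are not in the protocol, and that cause of amblyopia has three categories (section 2.2), not two.

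**Conclusion.** The point stands at modest severity. The stated general approach cannot show whether the treatment effect differs between subgroups, and no explicit caution covers a positive overall result, where misleading contrasts are most likely.

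The large figures (about 46% per factor, about 85% across seven, about 80% across five) hold only if a uniform effect of 0.075 logMAR is true and readers compare subgroup p-values. They assume binary, 50:50, independent factors. Unequal splits raise them, and moderate correlation between factors barely lowers them. The comparators are 5% per factor and about 30% across seven. With no true effect the gain is a few percentage points at most.

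The primary estimate, its type I error, the power and the sample size are untouched, and no claim is formally tied to a subgroup.

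**What to change.** In section 6.2.3, state that differences between subgroups will be judged by one ANCOVA per factor on all patients, with treatment, baseline acuity, the factor and the treatment-by-factor interaction. Preferably keep age, the acuity factors and length of prior treatment continuous for the test. For acuity at randomization, the factor is then the baseline covariate already in the model. Report each interaction estimate with its 95% confidence interval, and give within-subgroup estimates with confidence intervals as description only. Apply the same caution whether or not the overall result is significant, and note that seven factors are examined without multiplicity control. The analysis plan should carry the same wording before outcome data are seen.

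The cost is wording only, with no extra patients or visits. The downside is low interaction power, about 38% for a 0.075 logMAR difference in effect, so a non-significant interaction must not be read as proof that effects are equal.
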